A TEAE is defined as an undesirable event not present prior to medical treatment, or an already present event that worsens either in intensity or frequency following the treatment. Each TEAE will be attributed to a treatment based on Investigator (or designee) judgment as well as on its onset date and time. An AE that occurs during the washout period between treatments will be considered treatment-emergent to the last treatment given. If an AE has a change in severity grade, the original AE will be given a resolution date and time of the time of severity grade increase or decrease and a new AE record will be initiated with the new severity grade, and the new AE record will use the resolved date/time of the previous record as the onset date/time. If an AE decreases in severity grade, the new AE record with less severity will be considered and counted as the same AE event of the previous record with worse severity under the same treatment group and period in the analysis. If the severity grade of an AE remains the same, the AE will be kept open through to resolution.

If the onset time of an AE is missing and the onset date is the same as the treatment dosing date, then the AE will be considered treatment-emergent in both the prior and current treatment. If the onset time of an AE is missing and the onset date does not fall on a dosing date, then the AE will be considered treatment-emergent for the last treatment administered. If the onset date of an AE is missing, then the AE will be considered treatment-emergent and attributed to the first treatment group on the

study, unless the onset date is known to have occurred within or between specific treatment periods. For an AE with multiple changes in severity, a new record with severity less or equal to its maximum severity will not be considered as a new event in the summary tables.

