Presyncope	X (XX%)	X (XX%)	X (XX%)	X (XX%)
Respiratory, thoracic and mediastinal disorders	X (XX%)	X (XX%)	X (XX%)	X (XX%)
Dry throat	X (XX%)	X (XX%)	X (XX%)	X (XX%)
Oropharyngeal pain	X (XX%)	X (XX%)	X (XX%)	X (XX%)
Sinus congestion	X (XX%)	X (XX%)	X (XX%)	X (XX%)
Sneezing	X (XX%)	X (XX%)	X (XX%)	X (XX%)
General disorders and administration site conditions	X (XX%)	X (XX%)	X (XX%)	X (XX%)
Fatigue	X (XX%)	X (XX%)	X (XX%)	X (XX%)
Thirst	X (XX%)	X (XX%)	X (XX%)	X (XX%)
etc.				

Note: * Adverse events are classified according to the MedDRA Version 21.1 by System Organ Class and Preferred Term.

TE = Treatment-emergent

If a TEAE decreased in severity grade, the new TEAE record with less severity was counted as the same TEAE event of the previous record with worse severity under the same treatment group.

Treatment A: A single dose of 0.5 mg repaglinide administered at Hour 0 on Day 1

Treatment B1: Multiple doses of 160 mg LOXO-292 BID from Day 1 to Day 9

Treatment B2: Multiple doses of 160 mg LOXO-292 BID on Day 10 with a single dose of 0.5 mg repaglinide coadministered on the morning of Day 10

Program: /CAXXXX/sas_prg/stsas/tab_PROGRAMNAME.sas DDMMYY YYYY HH:MM

Programmer Note: Sort by decreasing frequency of system organ class and by preferred term within a system organ class of Overall column. For each subject, please sort the AEs with same verbatim and preferred term by onset date/time. For any pair (e.g., AE_S1, AE_S2) of these AEs (for same subject, same verbatim and preferred term), if the onset date/time of AE_S2 = resolved date/time of AE_S1 and the grade of AE_S2 < the grade level of AE_S1, then mark the AE_S2 with a flag like EVAUL_FLG = "N". Then, for AE analysis (summary tables), please exclude the ones with EVAUL_FLG = "N". Won't repeat this comment again.

Table 14.3.1.2 Treatment-Emergent Adverse Event Frequency by Treatment, Severity Grade, and Relationship to Study Drugs - Number of Subjects Reporting Events (Safety Population)

TE Adverse Event*	Treatment	Number of Subjects with Adverse Events	Severity Grade					Relationship to LOXO-292		Relationship to Repaglinide	
			1	2	3	4	5	Related	Not Related	Related	Not Related
Dizziness	A	X	X	X	X	X	X	X	X	X	X
Dry eye	B1	X	X	X	X	X	X	X	X	X	X
Dry mouth	A	X	X	X	X	X	X	X	X	X	X
	B1	X	X	X	X	X	X	X	X	X	X
Dry throat	B1	X	X	X	X	X	X	X	X	X	X
Ear pain	A	X	X	X	X	X	X	X	X	X	X
Fatigue	B2	X	X	X	X	X	X	X	X	X	X
Treatment A	XX	X	X	X	X	X	X	X	X	X	X
Treatment B1	XX	X	X	X	X	X	X	X	X	X	X
Treatment B2	XX	X	X	X	X	X	X	X	X	X	X

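### The severity-change sentence in SAP 7.3 has no segment limit, so an unresolved event that eases and re-worsens in a later segment can be left out of that segment's TEAE count, contrary to the SAP's own definition and programmer note

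*SAP*

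**What the plan says.** All rules below are in SAP 7.3 unless stated otherwise.

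- **Definition.** A TEAE is an event absent before treatment, or "an already present event that worsens either in intensity or frequency following the treatment".
- **Record splitting.** A change of grade closes the current record and opens another, and "the new AE record will use the resolved date/time of the previous record as the onset date/time".
- **Falling grade.** A record of lower grade "will be considered and counted as the same AE event of the previous record with worse severity under the same treatment group and period".
- **Multiple changes.** For an event with several grade changes, "a new record with severity less or equal to its maximum severity will not be considered as a new event in the summary tables". No treatment, period or segment is named.
- **Maximum grade.** If a subject has the same TEAE at several grades, only the worst is counted, separately for each treatment.
- **Programmer note to Table 14.3.1.1 (SAP 10.3).** For the same subject and term, a record is excluded from the summaries "if the onset date/time of AE_S2 = resolved date/time of AE_S1 and the grade of AE_S2 < the grade level of AE_S1".

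For adverse events, Treatment B is split into B1 (Days 1 to 9, LOXO-292 alone) and B2 (Day 10, with repaglinide) (SAP Table 5.1). The TEAE tables show A, B1, B2 and overall.

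**The concern.** Record splitting gives a rise in grade after the Day 10 dose a Day 10 onset, and the definition makes it a TEAE of B2. The multiple-changes sentence then looks back over the whole life of the event. If the grade was as high or higher at any earlier time, even in B1, the new record is not a new event and B2 does not show it. The programmer note compares a record only with the one just before it, so it never removes a rise.

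Secondary objective 2 asks about tolerability with and without repaglinide, and the B1 and B2 columns are how the tables answer it. Where the sentence has this effect, it lowers the later segment's count. Two programmers, one working from the text and one from the note, could deliver different tables.

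**Working it through.** The plan states no figure on this point, so there is none to reproduce. The check applies the three rules to the same records.

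**Setting.** One continuous event has grades g1, g2, …, gk. All records before the last start in B1, and the last starts on Day 10 after repaglinide. Consecutive grades differ, because only a grade change opens a record.

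**Rules as tests on the last record**

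- Definition: counted in B2 if gk > g(k−1).
- Multiple-changes sentence: left out if there are at least two changes and gk ≤ max(g1, …, g(k−1)).
- Programmer note: left out only if gk < g(k−1).

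**Example (hypothetical).** Dry mouth is grade 2 on Day 3, grade 1 on Day 6, and grade 2 again on Day 10.

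- Definition: 2 > 1, so it is counted.
- Sentence: two changes and 2 ≤ max(2, 1) = 2, so it is left out.
- Note: 2 < 1 is false, so it is kept.

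The B2 count is 1 under the definition and the note, and 0 under the sentence.

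**All three-record paths with grades 1 to 3 that rise on Day 10**

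| Path | Definition | Note | Earlier maximum | Sentence |
|---|---|---|---|---|
| 2-1-2 | counted | kept | 2 | left out |
| 3-1-2 | counted | kept | 3 | left out |
| 3-1-3 | counted | kept | 3 | left out |
| 3-2-3 | counted | kept | 3 | left out |
| 2-1-3 | counted | kept | 2 | kept |
| 1-2-3 | counted | kept | 2 | kept |

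The definition and the note keep 6 of 6; the sentence leaves out 4 of 6. For four-record paths the definition and the note keep 12 of 12, and the sentence leaves out 10 of 12 (it keeps 1-2-1-3 and 2-1-2-3). Two-record paths (1-2, 1-3, 2-3) have only one change, so the sentence does not apply and none is lost. These are counts of possible paths, not probabilities.

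**A second ambiguity.** The table takes the maximum over earlier records, which is the ordinary reading. If the maximum were taken to include the new record, no record could exceed it, and all 6 and all 12 would be left out. The term therefore needs a definition.

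**Why only boundaries matter.** The tables count a subject once per category, at the worst grade per treatment. Within one segment, leaving out a record at or below the earlier maximum changes neither the incidence nor the maximum-grade count. Those counts change only when the earlier peak lies in a different segment.

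**Size.** 1/16 = 6.25 percentage points per affected subject, with the 16 subjects of SAP Section 5 all dosed in B2. A preferred-term cell changes only if the subject has no other B2 record of that term. The row for subjects with any TEAE changes only if the subject has no other B2 TEAE.

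**After the change proposed below.** The Day 10 record has no earlier record in B2, so the sentence no longer reaches it, and 6 of 6 paths stay in B2.

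The check concerns intensity only. A change in frequency at a constant grade opens no new record: "If the severity grade of an AE remains the same, the AE will be kept open through to resolution".

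**The case against.** The best defence is that the missing limit is a drafting slip. The falling-grade rule is confined to the same treatment and period, the maximum-grade rule works per treatment, and the footnotes of Tables 12-1, 14.3.1.1 and 14.3.1.2 speak of a decrease under the same treatment group. Tables built from the programmer note would place the example in B2. The safety analysis has no inferential statistics, all adverse events are listed, and serious events have their own table. This explains how the gap arose and shows that its consequences are small. It does not settle which instruction governs, and the sentence as written gives the wrong B2 count.

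A reader might also infer more than the documents support:

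- *Events that first start on Day 10 are lost.* The sentence covers only an event with several grade changes. A first onset has no earlier record, and a recurrence after full resolution is a new event. If the onset time is missing on a dosing date, "then the AE will be considered treatment-emergent in both the prior and current treatment", so B2 keeps it.
- *Any worsening in a later segment is lost.* A single rise stays, as does a rise to a new maximum on the ordinary reading. Loss needs one unresolved event with at least two changes, easing and then re-worsening in a later segment to no more than its earlier peak. For an event that peaks and eases under A and then re-worsens in B1, both steps must fit into the 24 hours before LOXO-292 starts.
- *Investigator opinion can move a Day 10 event into B1.* The SAP says "Each TEAE will be attributed to a treatment based on Investigator (or designee) judgment as well as on its onset date and time". The two criteria are joined; nothing lets judgment override a known onset time or equates it with causality, which is recorded separately. At most a tie-breaker is missing, and that contradicts neither the definition nor the programmer note.
- *Every omitted record costs 6.25 points.* That is the largest effect per subject, not the effect of each record.

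**Conclusion.** The point holds in a narrow form. For an unresolved event that eases in one segment and re-worsens in a later one to a grade no higher than its earlier peak, the last sentence of the adverse-event rules in SAP 7.3 removes it from the later segment's TEAE count. The definition counts it, and the programmer note keeps it. The loss is at most 1 of 16 subjects per affected subject, assuming all 16 are dosed in B2. How often it would occur cannot be read from the documents and is probably low. It touches the TEAE summary tables (12-1, 14.3.1.1 and 14.3.1.2), not the listings or the primary PK analysis. It is worth correcting because it bears on secondary objective 2 and one clause removes the conflict. The conclusion rests on reading the maximum as that of the earlier records; the literal alternative would widen the loss.

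**What to change.** In SAP 7.3:

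1. Limit the multiple-changes sentence by adding *within the same treatment segment (A, B1 or B2)*.
2. Define maximum severity as that of the earlier records in that segment.
3. State that a record starting in a later segment at a higher grade than the record just before it is a TEAE of the later segment.
4. Align the Table 14.3.1.1 programmer note and the footnotes of Tables 12-1, 14.3.1.1 and 14.3.1.2 with this wording.

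Keep the existing rules for missing onset dates and times. The cost is a few words in the SAP and a small programming check, with no new data. B1 or B2 counts may rise slightly where such events occur.

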7.4 Clinical Laboratory Tests (Serum Chemistry, Hematology, Coagulation, and Urinalysis)

All clinical laboratory test results will be presented in by-subject data listings, however, only serum chemistry, hematology, coagulation and urinalysis values will be summarized.

Hematology, coagulation, serum chemistry and urinalysis tests will be conducted at the following time points:

Table 7.4 Lab Test Time Points

Period	Period Day
Screen	Screening*
1	Day -1 (check-in)*
2	Day 1**
2	Day 3***
2	Day 6**
2	Day 10**
2	Day 11***

* performed following a fast of at least 12 hours
** performed prior dosing
*** performed at the end of Period 2 or prior to ET

Out-of-normal range (OOR) flags will be recorded as follows: high (H) and low (L) for numerical results and did-not-match (*) for categorical results. If a value fails the reference range, it will automatically be compared to a computer clinically significant (CS) range suggested by the PI (Celerion SOP GSOP.10.1028). If the value falls within the computer CS range, it will be noted as "N" for not clinically significant. If the value fails (i.e., falls outside of the CS range) the computer CS range, it will be flagged with a "Y" which prompts the PI to determine how the OOR value should be followed using 4 Investigator flags: "N", not clinically significant, "R", requesting a recheck, "^", checking at the next scheduled visit, or "Y", clinically significant. To distinguish the PI flag from the CS range flags, the PI flags "N" and "Y" will be presented as "-" and "+" in the data listings, respectively. Additionally, a derived flag based on a search of the PI comments for a comment of "CS" or "Clinically Significant" will be used. The derived flag will be populated with "+" if the positive clinically significant determination is found in the comments for cases when the PI flag is populated with a "^" or an "R". In addition, CTCAE, version 5.0 grading (found in NCI CTCAE guidance) will be applied to all out of range lab values deemed clinically significant by the Investigator (or designee) which are recorded as AEs.

Out-of-range values and corresponding recheck results will be listed. Other lab results within this panel and time point will also be listed for this subject. Results that are indicated as CS by the PI (either in the PI flag or in PI comments) will be listed in the table. Out-of-range values laboratory value results which are indicated as CS by PI will be reported as AEs.

For all laboratory values that are numeric, descriptive statistics (n, mean, SD, minimum, median, and maximum) will be presented for each laboratory test by treatment and time point. Change from baseline in Treatment B (defined below) will also be summarized. Postdose unscheduled events or rechecks will not be summarized. Similarly, ET results will not be included in summaries.

For each laboratory test, a shift table will be developed comparing the frequency of the results at baseline (above normal, normal, or below normal) to postdose results. For urinalysis tests, the categories are normal and outside normal.

Baseline is Day -1 of Treatment A (Period 1) and Day 1 predose of Treatment B (Period 2), and is the last non-missing predose measurement prior to dosing of LOXO-292, including rechecks and unscheduled assessments.

7.5 **Blood Glucose Monitoring**

Blood glucose monitoring will be performed at the following time points:

Table 7.5 Glucose Monitoring Time Points

Period	Period Day	Study Hour
1	Day 1	0*
1	Day 1	1
1	Day 1	2
1	Day 1	4
1	Day 1	6
1	Day 1	9
2	Day 10	0*
2	Day 10	0.5
2	Day 10	1
2	Day 10	1.5
2	Day 10	2
2	Day 10	3
2	Day 10	4
2	Day 10	6
2	Day 10	9
* performed prior dosing		

Descriptive statistics will be reported for blood glucose determinations and change from baseline by treatment and time point. Baseline is Day 1 predose of Treatment A (Period 1) and Day 10 predose of Treatment B (Period 2) and is the last non-missing predose measurement prior to dosing of repaglinide including rechecks and unscheduled assessments. Postdose rechecks, unscheduled assessments, and ET results will not be used for calculation of descriptive statistics. All blood glucose results will be listed by subject.

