having blood drawn. BP and HR will be measured using the same arm for each reading. Subjects are to be supine for 5 minutes prior to vital sign assessments.

g: Samples for serum chemistry will be obtained following a fast of at least 12 hours at screening and at Check-in (Day -1, Period 1); at other scheduled times, serum chemistry tests will be performed after at least an 8-hour fast. However, in case of dropouts or rechecks, subjects may not have fasted for 12 or 8 hours prior to the time that the serum chemistry sample is being taken.

h: AEs and SAEs will be recorded beginning at informed consent. All AEs will be recorded throughout the study (i.e., from signing of the ICF until EOS or ET if the subject discontinues from the study and does not complete a follow up call), either as subject medical history (if the event is reported as beginning prior to signing of the ICF or if the event occurs prior to study drug administration on Day 1 of Period 1 and is assessed as not related to study procedures by the PI [or designee]) or as AEs (if the event occurs after signing of the ICF but prior to study drug administration on Day 1 of Period 1 and is assessed as related to study procedures by the PI [or designee], or if the event occurs after study drug administration on Day 1 of Period 1 regardless of relationship to study drug). From EOT or ET through EOS only AEs assessed as related to study drug by the PI (or designee) are to be reported. All SAEs that develop from the time of ICF signing until EOS (or ET if the subject discontinues from the study and does not complete a follow up call) are to be reported.

i: 

j: 

k: 

l: All glucose measurements will be done with a glucose monitor and will be performed by finger stick.

m: Glucose will be administered immediately following repaglinide dosing and at approximately 1 hour postdose (after the PK sample).

n: To be performed at the EOT (Day 11, Period 2), or prior to ET from the study. EOT is defined as when the subject is released from the CRU following completion of all assessments through Day 11 of Period 2. ET is defined as when the subject is released from the CRU if the subject terminates the study early. Vital Sign, ECG, and Safety laboratory results for serum chemistry, hematology, coagulation, and urinalysis are to be available for review by the PI or designee prior to subject release from the CRU at the EOT or ET visit.

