12.2 Dose Modification

The dose and administration of the study drugs to any subject may not be modified. If necessary a subject must be discontinued for the reasons described in [Section 11.3](#).

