7. SAFETY

No inferential statistics are to be performed for the safety analysis.

All clinical safety and tolerability data will be listed by subject and assessment time points, including rechecks, unscheduled assessments, and early termination (ET), chronologically.

Continuous variables will be summarized using n, mean, SD, minimum, median, and maximum. Frequency counts will be reported for categorical data when appropriate.

The level of precision will be presented as follows: “n” as an integer, minimum/maximum in same precision as in the database, mean/median in one more precision level than minimum/maximum, and SD in one more precision level than mean/median.

Where individual data points are missing because of dropouts or other reasons, the data will be summarized based on reduced denominators.

When change from baseline is calculated, baseline is the last scheduled assessment before dosing at Period 1, including rechecks and unscheduled assessments, whichever is later, unless otherwise specified in the sections below. Rechecks, unscheduled assessments and ET measurements taken after first dosing will not be used in the summarization.

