7.6 Vital Signs (Blood Pressure, Pulse Rate, Respiration Rate, and Temperature)

Vital signs will be performed at the following time points:

Table 7.6 Vital Signs Time Points

Period	Period Day	Study Hour	Assessment
Screen	Screening		HR, BP, RR, T
1	Day -1	Check-in*	HR, BP, RR
1	Day 1	0**	HR, BP, RR, T
1	Day 1	0.75	HR, BP, RR
1	Day 1	2	HR, BP, RR
1	Day 1	4	HR, BP, RR
2	Day 1	0**	HR, BP, RR

Period	Period Day	Study Hour	Assessment
2	Day 1	0.75	HR, BP, RR
2	Day 1	2	HR, BP, RR
2	Day 1	4	HR, BP, RR
2	Day 2	0**	HR, BP, RR
2	Day 3	0**	HR, BP, RR
2	Day 4	0**	HR, BP, RR
2	Day 5	0**	HR, BP, RR
2	Day 6	0**	HR, BP, RR
2	Day 7	0**	HR, BP, RR
2	Day 8	0**	HR, BP, RR
2	Day 9	0**	HR, BP, RR
2	Day 10	0**	HR, BP, RR
2	Day 10	0.75	HR, BP, RR
2	Day 10	2	HR, BP, RR
2	Day 10	4	HR, BP, RR
2	Day 11	24***	HR, BP, RR, T

* performed within 24 hours prior dosing
 ** performed prior dosing
 *** performed at the end of Period 2 or prior to ET

Descriptive statistics will be reported for vital sign measurements (blood pressure, pulse, and respiration rate) and change from baseline by treatment and time point. Baseline is Day 1 predose of Treatment A (Period 1) and Day 1 predose of Treatment B (Period 2) and is the last non-missing predose measurement prior to dosing of repaglinide (Treatment A) or LOXO-292 (Treatment B), including rechecks and unscheduled assessments. Postdose rechecks, unscheduled assessments, and ET results will not be used for calculation of descriptive statistics. All vital signs results will be listed by subject.

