7.7 ECG (Heart Rate, PR, QRS, QT, and QTcF [QT with Fridericia correction])

Single 12-lead ECGs will be performed at the following time points:

Table 7.7: ECG Time Points

Period	Period Day	Study Hour
Screen	Screening	
1	Day -1	Check-in*
1	Day 1	0**
1	Day 1	2
2	Day 1	0**
2	Day 1	2

Period	Period Day	Study Hour
2	Day 2	0**
2	Day 3	0**
2	Day 4	0**
2	Day 5	0**
2	Day 6	0**
2	Day 7	0**
2	Day 8	0**
2	Day 9	0**
2	Day 10	0**
2	Day 10	2
2	Day 11	24***

* performed within 24 hours prior dosing
** performed prior dosing
*** performed at the end of Period 2 or prior to ET

Descriptive statistics will be reported for ECG parameters and change from baseline by treatment and time point. Baseline is Day 1 predose of Treatment A (Period 1) and Day 1 predose of Treatment B (Period 2) and is the last non-missing predose measurement prior to dosing of repaglinide (Treatment A) or LOXO-292 (Treatment B), including rechecks and unscheduled assessments. Postdose rechecks, unscheduled assessments, and ET results will not be used for calculation of descriptive statistics. All ECG interval parameters will be listed by subject and time point of collection with QTcF > 450 msec and change from baseline > 30 msec flagged.

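### Early-termination values are left out of the safety summary and laboratory shift tables, so an abnormality first seen at withdrawal is counted in no shift table

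*SAP*

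**What the plan says.** The general rule is in SAP section 7: "Rechecks, unscheduled assessments and ET measurements taken after first dosing will not be used in the summarization". Section 7.4 repeats it for laboratory tests ("Similarly, ET results will not be included in summaries") and in the sentence before also rules out postdose unscheduled values and rechecks. Sections 7.6 and 7.7 use the same sentence for vital signs and ECG: "Postdose rechecks, unscheduled assessments, and ET results will not be used for calculation of descriptive statistics".

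Shift tables are planned for laboratory tests only (14.3.5.2, 14.3.5.4, 14.3.5.6). Section 7.4 says that "a shift table will be developed comparing the frequency of the results at baseline (above normal, normal, or below normal) to postdose results". That sentence has no ET rule of its own, so the section 7 rule governs. The shared table shell has fixed-day rows and no ET row.

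On collection, the protocol's Period 2 flow chart pairs the two visits: "To be performed at the EOT (Day 11, Period 2), or prior to ET from the study". SAP Tables 7.4, 7.6 and 7.7 carry this over as a footnote to Day 11, "performed at the end of Period 2 or prior to ET".

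Protocol 12.2 states: "The dose and administration of the study drugs to any subject may not be modified". A subject who cannot continue is discontinued, and Protocol 11.3 then sends withdrawn subjects through the ET procedures.

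The SAP keeps ET values elsewhere:
- Section 7 lists all safety data by subject, ET included, and handles dropouts with reduced denominators, so earlier scheduled values stay in the summaries.
- The shell for the out-of-range laboratory tables (14.3.4.1 to 14.3.4.3) sorts early-termination values in with the others.
- Table 14.3.4.4 shows every time point for a subject and test with a value that the investigator calls clinically significant. Such out-of-range values are also reported as adverse events.
- The ECG listing flags QTcF above 450 msec and changes above 30 msec.

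**The concern.** Because doses cannot be adjusted, a subject who does not tolerate LOXO-292 can only leave. The later scheduled values are then missing for a reason that may be the very outcome being tabulated, and the Day 11 rows describe completers. The ET panel is collected for these subjects but reaches none of the summary or shift tables. The same holds for an unscheduled sample that prompted the withdrawal.

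Safety and tolerability of multiple-dose LOXO-292 is a stated secondary objective. Protocol 8.1.1 lists liver-test increases among the theoretical risks and reports Grade 3 or higher liver-test abnormalities in a small number of patients. The shift tables are where a reader looks for a count of subjects who moved from normal to high, and here that count can be too low.

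**Working it through.** The documents give no figure on this point, so there is nothing to reproduce. The check sets the schedule against the exclusion rule and adds an illustration.

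**Last tabulated value for a withdrawn subject.** SAP Table 7.4 schedules laboratory tests in Period 2 on Day 1 (predose, the LOXO-292 baseline), then Days 3, 6, 10 and 11. With ET, unscheduled and recheck values excluded:

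| Subject stops | Last post-baseline laboratory value tabulated |
|---|---|
| Day 1 after dosing, or Day 2 | none |
| After the Day 3 sample, before the Day 6 sample | Day 3 |
| After the Day 6 sample, before the Day 10 sample (so any of Days 7 to 9) | Day 6 |
| After the Day 10 sample, before Day 11 | Day 10 |

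The longest gap is Day 6 to Day 10, four days of twice-daily dosing. For ECG and vital signs, Tables 7.6 and 7.7 schedule a predose measurement on every day from 1 to 10, so the last tabulated value is normally within about a day of ET.

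**Effect on the final row (illustration).** Assume that k of 16 subjects stop early, each is first abnormal at ET, nobody is replaced, and no completer is abnormal on Day 11. The planned Day 11 row shows 0/(16 − k). A row that counts ET values shows k/16.

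| k | Planned Day 11 row | ET values counted |
|---|---|---|
| 1 | 0/15 | 1/16 = 6.25% |
| 2 | 0/14 | 2/16 = 12.5% |
| 3 | 0/13 | 3/16 = 18.75% |

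Protocol 10.1 allows replacement. If one such subject is replaced by a completer with normal results, the Day 11 row reads 0/16, against 1/17 = 5.9% of all treated subjects, and the denominator no longer hints at the withdrawal.

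**How often the rule would bite.** The documents give no withdrawal rate. For an assumed rate d, P(at least one ET) = 1 − (1 − d)^16 and P(at least two) = 1 − (1 − d)^16 − 16d(1 − d)^15.

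| Assumed d | At least one | At least two |
|---|---|---|
| 2% | 27.6% | 4.0% |
| 5% | 56.0% | 18.9% |
| 10% | 81.5% | 48.5% |
| 15% | 92.6% | 71.6% |
| 20% | 97.2% | 85.9% |

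These are chances of early termination for any reason. The chance of one with a new abnormality at ET is smaller, and the documents give no basis for it.

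**The case against.** The strongest reply is that little is hidden. There are 16 confined subjects, each listed individually, with no inferential safety statistics. ET laboratory values appear in the Section 14 out-of-range tables, clinically significant ones become adverse events, and the disposition tables give reasons for discontinuation. All of this stands. It leaves one narrower gap: the listings give no counts, and the adverse-event route depends on the investigator's judgement of significance.

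Two stronger readings are tempting, and the documents support neither. A reader might infer that withdrawn subjects disappear from the safety tables. They do not, since their earlier scheduled values stay in. A reader might also infer that the SAP contradicts itself by placing ET in the Day 11 row and then excluding it. The footnote says when a procedure is done and does not define an analysis window. In Table 7.4 it is also attached to Day 3, which makes it a poor basis for an analysis rule. The analysis rule itself is the same in sections 7, 7.4, 7.6 and 7.7.

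Three further objections also stand:
- With no laboratory test scheduled between Days 6 and 10, an abnormality first seen at an ET visit on Day 8 cannot have caused the withdrawal. Only an unscheduled sample could have shown it earlier, so a remedy that restores ET values alone would be incomplete.
- The related Grade 3 or higher liver-test abnormalities in patients arose 20 to 56 days after starting LOXO-292. Dosing here lasts 10 days, so that history is weak evidence of what to expect.
- Pooling ET into Day 11 would mix LOXO-292 alone with values after repaglinide, a split that the SAP keeps for adverse events as B1 and B2. The protocol also warns that chemistry samples from dropouts may not be fasted.

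Finally, the shells are declared to be general layouts, so the missing ET row is weak evidence alone. The case rests on the explicit text of section 7.

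**Conclusion.** The point holds as a cheap improvement to the tables that serve the secondary safety objective. ET, postdose unscheduled and recheck values are excluded from the summary tables and, through the section 7 rule, from the laboratory shift tables. An abnormality first seen at ET is therefore counted in no shift table, though it remains in the listings and, if an out-of-range laboratory result, in Tables 14.3.4.1 to 14.3.4.3.

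The gap is largest for laboratory tests, where a subject stopping on Days 7 to 9 is last tabulated on Day 6. It is small for ECG and vital signs. Each affected subject is 1/16 = 6.25% of the planned sample. The 0/15 against 1/16 comparison is illustrative: the number of withdrawals and their results are assumed. The primary pharmacokinetic analysis does not depend on any of this.

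**What to change.** 1. Keep every by-day row, Day 11 included, as planned.
2. Add a worst post-baseline row to laboratory shift Tables 14.3.5.2, 14.3.5.4 and 14.3.5.6, using scheduled, ET, unscheduled and recheck values. Define worst separately for high and low, since one subject can have both.
3. Show ET values in a separate row, labelled ET / last on-treatment and not pooled with Day 11, in Tables 14.3.5.1, 14.3.5.3, 14.3.5.5, 14.3.5.8 and 14.3.5.9, with the number of ET values in a footnote.
4. Amend the exclusion sentences in SAP sections 7, 7.4, 7.6 and 7.7 so that they apply to the by-day rows only, and state the rule for shift tables explicitly.
5. In the same edit, correct the end-of-period footnote on Day 3 in Table 7.4, and reconcile Day 9 in the shift-table shell with Day 10 in Table 7.4.

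The cost is some SAP wording and one derived row per table. No new data are needed, because the ET panel is already collected. The added rows mix different days on drug, LOXO-292 alone with coadministration, and possibly non-fasted chemistry, and a footnote should say so. A worst-value row also picks up more abnormalities in subjects who were sampled more often.
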